## 3 Study Design

### 3.1 Subject Selection

#### 3.1.1 Inclusion Criteria

- Men with DM, type 2
- $\geq 18$  years old

#### 3.1.2 Exclusion Criteria

- Any evidence of end-organ failure attributed to DM (assessed based on medical history / patient history alone)
  - Loss of fingers / toes
  - CKD Stage IV or greater
  - Retinopathy
  - Myocardial infarction
  - Cerebrovascular accident
  - Indwelling penile prosthesis or prior history of penile prosthesis
- Peyronie's disease at baseline

### 3.2 Setting

The current study will be conducted at the Mayo Clinic in Rochester, MN Department of Urology. All patients will be recruited from mailers to Mayo Clinic patients with a known history of DM.

### 3.3 Recruitment

Patients with a known history of DM, type II will be sent a mailer and offered participation if meeting inclusion / exclusion criteria. Those interested in proceeding with the trial will be invited to meet with a study coordinator. At that time, the details of the study itself will be reviewed with the potential participant. Financial incentives will be provided, to include \$100 for the first visit and \$250 for each follow-up visit if meeting inclusion / exclusion criteria. Participants will also be given a RestoreX® device at no charge. Patients will not be charged for any visits related to the study, and no labs or other testing will be obtained which require payment.

Patients may also be recruited directly from the DM clinical practice, however, it is not anticipated that this will be the primary source of recruitment.

### 3.4 Consent and Enrollment

Patients wishing to enroll in the study will be given the opportunity to meet with the study coordinator to further review study details and formal consent.

Patients that would like additional time to consider their participation will be given other opportunities to meet with the study coordinator if desired. If the patient expresses interest in participating at any of these times, a formal consent will be reviewed (see **Attachment – Consent Form**).

At enrollment, all participants will be assigned a study identifier, with a master list maintained in a password protected database (Mayo server – RAVE database) linking the patient to the identifier. A total of 30 patients will be enrolled into each arm of the study for a total of 120 patients enrolled overall. It is estimated that up to 360 patients will need to be screened to enroll the 120 patients.

### 3.5 Study Schema

All patients will have been previously seen at Mayo Clinic for a condition of DM. Following enrollment, key factors relating to their underlying condition will be abstracted from the chart by a study coordinator, including age, duration of disease (if known), number of DM medications, use of insulin, most recent fasting glucose and HbA1c, creatinine, and testosterone, HOMA1-IR, HOMA2-IR, and BMI. If any of these variables are not available, no additional attempts will be made to retrieve the information.

At the initial appointment, patients will also undergo a penile length assessment by a urology provider and Men's Health Nurse and receive questionnaires (IIEF-15 and disease specific history)

Once consent and study assessments are completed, the patients will be randomized into one of four groups:

1. PTT for 30 min 2x/day x 3 months, followed by no treatment x 3 months
2. PTT for 30 min 2x/day x 3 months, followed by once weekly (30 minutes) x 3 months
3. PTT for 30 min 2x/day x 6 months
4. Control (no treatment)

Patients in the treatment arm will record a daily journal of their usage of the device. Patients will then begin using the device as instructed for the times appropriate to their group.

After 3 months of using the device (+1.5 months permitted), patients will return for subsequent assessments (see below) and a follow-up questionnaire. At this time, patients will be encouraged to report any adverse events. They will also be requested to bring their device back to the clinic to review proper usage and any questions on the device. After completion of the subsequent assessments, patients will begin the second phase of the trial.

After 6 months (+ 1.5 months permitted) patients will return to the clinic to undergo final assessments, which are identical to the 3-month assessments.

Since participants are being asked to travel to Mayo Clinic for subsequent assessments, we will provide a remuneration amount of up to \$600. The purpose is to assist participants in their travel to and from Mayo Clinic. Those that provide consent will be provided \$100 after their baseline assessment. After their second and third visits (3 and 6-months, respectively), they will receive \$250 for a possible total of \$600.

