## 2 Study Objectives

### 2.1 Primary Objective

1. The primary objective is to assess penile length pre and post completion of RestoreX® traction therapy compared to control groups (no treatment) of DM subjects.

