### 4.2 3 Month Visit

- Penile length assessment
- Questionnaires
  - 3 month
  - IIEF-15
- Device usage diary retrieved from treatment group
- Device usage diary given to all participants

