#### 4.4 Assessment of Length

Penile length measurements will be obtained by a member of the clinical team using a measurement from the pubic symphysis to the corona of the glans penis. Measurements will be obtained at baseline and at the 3 and 6 month follow-ups.

See **Attachments – Device Usage Diary, Disease Specific History, IIEF-15, Questionnaire 3 Month and 6 Month**

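### The plan does not mask the staff who read penile length at months 3 and 6, and it lists that reading first at each visit without requiring it to come first

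*Combined protocol and SAP*

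**What the plan says.** - **Outcome and comparator.** Section 2.1: "The primary objective is to assess penile length pre and post completion of RestoreX® traction therapy compared to control groups", the control being no treatment. The Study Summary and section 3.5 describe the control as using no traction. No sham device is mentioned.
- **Who measures.** For the first appointment, section 3.5 names a "penile length assessment by a urology provider and Men's Health Nurse". Section 4.4 covers baseline, month 3 and month 6 together: "Penile length measurements will be obtained by a member of the clinical team". Neither section says whether the measurer may know the group.
- **Baseline timing.** Section 3.5: "Once consent and study assessments are completed, the patients will be randomized into one of four groups". Baseline length is therefore read before allocation.
- **Month 3.** Section 3.5 says of patients: "They will also be requested to bring their device back to the clinic to review proper usage and any questions on the device". Section 4.2 lists the length assessment first, then the questionnaires, then "Device usage diary retrieved from treatment group" and "Device usage diary given to all participants".
- **Month 6.** Section 3.5 calls for "final assessments, which are identical to the 3-month assessments". Section 4.3 again lists length first and diary retrieval last.
- **Masking.** The table of contents has no blinding section, and no section from the Study Summary to the References mentions a masked or independent assessor.

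**The concern.** Length is read by hand, by a member of staff. Patients cannot be masked against a no-treatment control, but the measurer can be. At month 3 a man who arrives with a device or a completed usage diary reveals his group to anyone present. The plan neither keeps the measurer away from these nor obliges the reading to precede them.

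Because baseline is read before allocation, knowledge of group would bear on the follow-up readings and so on the change from baseline. A tendency to read slightly longer in traction patients would be indistinguishable from lengthening caused by the device. Section 5.2 offers no protection. The traction versus no-traction comparison, the three compliance-based analysis sets and the normalization by baseline length all use the same readings.

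**Working it through.** **1. Search for masking.** The text from the table of contents to the References was read for any blinding, masking, independent assessor or restriction on who may measure. None was found. The nearest candidate is section 5.1, which keeps information de-identified. That governs stored data and does not hide the group from the person examining the patient.

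**2. Search for a required order.**

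| Source | What it gives | Is an order required? |
|---|---|---|
| 3.5, month 3 | Assessments, adverse-event reporting and device review, then the second phase | Only that assessments precede the second phase |
| 4.2 | Length first, diary retrieval later; device review not listed | No, a bullet list |
| 4.3 | Length first, diary retrieval last | No, a bullet list |
| 4.5, Table 1 | Activities by visit | No |

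Length is thus listed first at both follow-up visits, but nothing obliges staff to take it first, and the device review is not placed relative to it.

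**3. What differs at month 6.** All participants are given a diary at month 3 (4.2), so a diary need not reveal the group at month 6. Masking is still not provided for.

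**4. Illustration of sensitivity.** The documents give no SD, alpha, effect size or bias size, so there is no figure of the plan's to reproduce beyond enrolment: 4 × 30 = 120 (section 3.4). *Assumed:* true effect zero, two-sided alpha 0.05, and a differential reading of d standard deviations of the analysed change, favouring traction.

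SE = √(1/n₁ + 1/n₂); rate = P(|Z + d/SE| > 1.96).

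- All traction against control, 90 v 30: SE = √(1/90 + 1/30) = 0.2108. For d = 0.25, d/SE = 1.186 and the rate is 0.220.
- One traction arm against control, 30 v 30: SE = √(1/30 + 1/30) = 0.2582. For d = 0.25, d/SE = 0.968 and the rate is 0.162.

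| Comparison | d = 0.1 | d = 0.25 | d = 0.5 |
|---|---|---|---|
| 90 v 30 | 7.6% | 22.0% | 66.0% |
| 30 v 30 | 6.7% | 16.2% | 49.1% |

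With an assumed 80% retention the rates are 7.1%, 18.6% and 56.4% (72 v 24), and 6.4%, 13.9% and 41.0% (24 v 24). A noncentral t calculation agrees to within 0.015. The 90 v 30 comparison describes a single common regimen only up to month 3, because the three traction arms then diverge.

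**The case against.** **Length is an objective measure and is already listed first.** Section 4.1 does class it as objective, and the lists in 4.2 and 4.3 do put it ahead of diary retrieval. A reader might infer that the plan has staff see the device or diary before measuring. The documents do not support that; they are silent on sequence. What stands is narrower: measuring first is neither required nor ruled out, and a measurement taken by hand can still be influenced by expectation.

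**The measuring roles conflict.** A reader might see a contradiction between 3.5 and 4.4. There is none: a urology provider and a nurse can both be members of the clinical team. The follow-up roles are simply less specific than the baseline ones.

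**The investigator invented the device (8.2), so the readings are compromised.** No section says that this person measures length, and 8.2 records a conflict-of-interest review. The most that follows is that a visible safeguard is worth more here.

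**The illustration proves serious bias.** It does not. Every shift in it is assumed, 0.1 SD matters little, and the documents give no basis for judging whether a larger shift is plausible.

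**The attachments may cover it.** They were not seen. Those named in section 4.4 are a diary, a history form and questionnaires; none is described there as a masking or measurement procedure.

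**Conclusion.** The point holds as a gap in protection: follow-up readers of the outcome in the primary objective are not masked, and nothing requires the reading to precede exposure to the device or diary. It does not show that bias will occur or how large it would be, and the illustrative rates do not set its importance. The case for change is that the safeguard is cheap, that no analysis in 5.2 can substitute for it, and that readings cannot be masked after they are taken. It should be made before follow-up measurement, but it does not invalidate the design. The conclusion rests on the protocol text reviewed, without the attachments or the removed front pages.

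**What to change.** Amend sections 3.5, 4.2, 4.3 and 4.4 along these lines:

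> At months 3 and 6, stretched penile length is measured before device review and diary collection, with device and diary out of the room. The measurement is made by existing clinical staff who took no part in that patient's allocation or device review and who are not told the group. Patients are asked beforehand not to reveal their group. Any unmasking is recorded.

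Two additions:

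- Name the same measuring roles for follow-up as for baseline, and use the word *stretched* in 4.4, as 3.6 and 5.2 already do.
- As a precaution, the inventor-investigator does not measure length.

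The timing of adverse-event questions should stay with the investigator. Masking does not need them deferred, and deferring them could mean measuring a man before anyone has asked about a device-related problem.

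**Cost.** Some separation of tasks among existing staff and one added data item (unmasking). If both a urology provider and a nurse measure, a third person must do the device review. No patient procedure is added. Masking fails if a patient speaks, so the protection is partial.

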### **3.6 Randomization Protocol**

Following enrollment and completion of the initial length assessment, patients will be categorized into the appropriate strata based on their baseline stretched penile length; strata categorized as <10 cm, 10cm-13cm, 13.1cm-16cm, >16cm stretched length. Each stratum will have a separate randomization table provided such that one of three possible outcomes will occur no less frequently than every other case. This is done to better account for baseline variables that may impact outcomes and to assist with matching groupings appropriately.

The explanation of which grouping the patient is assigned will then be reviewed, and if the patient subject is assigned to the treatment group, a RestoreX® device will be provided.

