## Study Summary

Title	Penile Length Restoration in Men with Diabetes Mellitus, Type II
IRB Protocol Number	18-006696
Methodology	Controlled randomized study
Overall Study Duration	3 years
Subject Participation Duration	6 months
Objectives	Evaluate the efficacy of the RestoreX penile traction device in restoring length loss secondary to diabetes mellitus
Number of Subjects	120
Diagnosis and Main Inclusion Criteria	Men with diabetes mellitus, type II
Study Device	RestoreX®, penile traction therapy
Duration of Exposure	Subjects in Groups 1-3 will use device for 3 months for 30 minutes, twice daily. Subjects in Group 4 will be control and will not use the device.  After the randomized period, subjects using the device will switch to not using the device (Group 1), using the device once weekly x 30 minutes (Group 2), or continuing to use the device twice daily x 3 months (Group 3).
Reference therapy	The use of the device will be compared against a control group using no traction therapy. Individuals will also be compared to themselves to evaluate changes from baseline.
Statistical Methodology	Stratification of subjects prior to randomization to assure an equal representation based on baseline penile length. Statistical comparisons will be made comparing total penile length prior to and following therapy. Comparisons of subjective questionnaire responses will also be made between groups and at the various time points captured.

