#### 5.2 Statistical Analysis

Analyses will be performed using comparisons within patients of same baseline penile stretch length and between groupings of varying lengths. Comparison of penile length between traction and no traction will be made, as well as reviewing historical records to increase statistical power. Comparison of length from baseline to post-traction for individual participants will also be reviewed.

The data will also be analyzed in three ways: 1- with all patients included, regardless of their compliance to utilize the device for the recommended treatment time, 2- with patients excluded if they failed to achieve 90% compliance with the recommended duration of treatment, 3- with patients excluded if they failed to achieve 75% compliance with the recommended duration of treatment. Factors which will also be included to determine compliance will include frequency and duration of use and whether or not the device was used correctly (black rods buried, amount of time white line showing).

Comparisons will also be made on other subjective and objective variables obtained including number of adverse events, complications, subjective responses to questionnaires, or other information. All data will be normalized by baseline stretched penile length.

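### Section 3.6's allocation rule has three outcomes, but the trial has four groups of 30, and its frequency clause does not give equal allocation within strata

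*Combined protocol and SAP*

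**What the plan says.** Section 3.5 (Study Schema) states that "the patients will be randomized into one of four groups": three traction schedules and an untreated control. The Study Summary describes the same Groups 1-4 and 120 subjects. Section 3.4 (Consent and Enrollment) gives the sizes: "A total of 30 patients will be enrolled into each arm of the study for a total of 120 patients enrolled overall".

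Section 3.6 (Randomization Protocol) defines four strata of baseline stretched length (<10, 10-13, 13.1-16 and >16 cm), each with its own randomization table. The tables are described by one rule: "one of three possible outcomes will occur no less frequently than every other case". The Study Summary gives the aim of the strata: "Stratification of subjects prior to randomization to assure an equal representation based on baseline penile length".

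Apart from the stratification, that rule is the only statement of how assignments are generated. No section gives an allocation ratio, a block size or a method of generating the sequence.

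**The concern.** Section 3.6 is where a reader would look for the rule behind the four stratum tables. Its number of outcomes disagrees with the number of groups, and its frequency clause does not match a 25% share per group. Someone who built a table from the section as written could not arrive at the design in Sections 3.4 and 3.5 without guessing.

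Two things are at stake. The first is arm size. The primary objective compares traction with control, and the device groups differ from one another only in their schedules after month 3, so the precision of each contrast depends on how the 120 patients are divided. The second is balance by baseline length, which is the stated purpose of stratifying. A rule that does not define allocation among four groups inside a stratum cannot assure it.

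**Working it through.** **Inputs.** Four groups (Study Summary, Section 3.5); 30 per arm and 120 in total (Section 3.4); three outcomes, one of them occurring "no less frequently than every other case", and four strata with separate tables (Section 3.6). The documents give no standard deviation, so precision is shown as a ratio to the plan, assuming equal standard deviations.

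**The plan's own figure.** 4 × 30 = 120, which reproduces. The planned share is 30/120 = 25% per arm.

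**Number of outcomes.** Three outcomes do not fit: 3 × 30 = 90, not 120, and 120/3 = 40 per arm, not 30. This does not depend on how the frequency clause is read.

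**Frequency clause, reading by reading.** Let n_s be the number of patients in stratum s, with the four n_s adding to 120.

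1. *The same single arm is favoured in every stratum.*
   - Its minimum is the sum of floor(n_s/2). That is 60 if all four n_s are even and 58 if all are odd, against a target of 30.
   - The other three arms average at most (120 − 60)/3 = 20 to (120 − 58)/3 = 20.7.
   - If those three split equally, the standard error between two of them, relative to 30 v 30, is √(30/20) = 1.22 or √(30/20.7) = 1.20.
   - Favoured arm v a smaller arm: 1/60 + 1/20 = 0.0667, the same as 1/30 + 1/30 = 0.0667, so the ratio is 1.00.
   - Traction v control at 3 months, assuming Groups 1-3 are pooled: the plan gives 1/90 + 1/30 = 0.0444. If control is the favoured arm, 1/60 + 1/60 = 0.0333, ratio √(0.0333/0.0444) = 0.87. If a traction arm is favoured, 1/100 + 1/20 = 0.060, ratio √(0.060/0.0444) = 1.16.

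2. *A different arm is favoured in each stratum.* Take four strata of 30, with 15 to the favoured arm and 5 to each other arm. Every arm then totals 15 + 5 + 5 + 5 = 30. Within each stratum, however, the split is 15:5:5:5, so arm and baseline length are tied together.

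3. *Each of three outcomes must occur at least every other case.* This needs 3 × 50% = 150% of the slots, which is impossible.

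4. *The three outcomes are the traction groups taken together.* Thirty per arm gives 90/120 = 75% traction, which satisfies the clause. But the clause then only bars two consecutive controls within a stratum. Taken alone it allows from 0 controls up to the sum of ceil(n_s/2), which is 60 to 62, and it says nothing about how Groups 1-3 share the remaining slots.

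**The fix, with blocks of 4.** Let r_s (0 to 3) be the patients in the last, incomplete block of each stratum. An arm's total is (120 − Σr_s)/4 plus between 0 and 4. The lowest case is r = (3,3,3,3): 108/4 + 0 = 27. The highest is r = (1,1,1,1): 116/4 + 4 = 33.

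**The case against.** The strongest reply is that the intended design is plain. Section 3.4 sets 30 per arm, Section 3.5 lists four groups, and 1:1:1:1 follows. If the three outcomes are the traction groups, Section 3.4 fixes the totals, Section 3.6 restricts runs of controls, and the frequency clause does not conflict with 30 per arm. This much stands: the target is recoverable, and under the pooled reading the clause is incomplete rather than contradictory. But Section 3.6 does not say that traction groups are pooled, and control is itself a result of the table, since a device is supplied only "if the patient subject is assigned to the treatment group". Even when granted, this reading leaves allocation among Groups 1-4 within a stratum undefined.

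A reader might infer that the rule is compatible with 30 per arm only under the pooled reading. That is not so: favouring a different arm in each of four equal strata also gives 30 per arm, at the price of balance by baseline length.

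A reader might also infer that the trial would in fact be split about 60/20/20/20. The documents do not support this. No section names a favoured arm, Section 3.6 says only that tables will be provided, and the tables are not shown.

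Nor does the three-outcome wording mean that control was dropped. Section 2.1 speaks of length "compared to control groups (no treatment) of DM subjects", and Section 5.2 states: "Comparison of penile length between traction and no traction will be made".

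**Conclusion.** The point holds as an internal contradiction in the text. A table with three outcomes cannot assign four groups, and none of the four readings of the frequency clause produces equal allocation to the four groups within each stratum.

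The numerical size is conditional. The figures of at least 58 to 60 in one arm and an average of at most 20 to 20.7 in the others require the same arm to be favoured in all four strata. The 20-22% larger standard error between two smaller arms further requires an equal split of the remainder and equal standard deviations. On those assumptions, with pooled traction groups, the effect on traction versus control at 3 months could go either way: about 13% smaller or about 16% larger. The clearest loss would therefore fall on comparisons between the smaller arms. No actual imbalance is claimed.

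**What to change.** Replace the allocation sentence in Section 3.6 with:

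> Within each of the four baseline-length strata, patients are allocated 1:1:1:1 to Groups 1-4 from a computer-generated list of randomly permuted blocks.

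In Section 3.4, change the 30 patients per arm to approximately 30 patients.

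The cost is two edits to the text and, if any tables were built on the present rule, regenerating them. Because of incomplete blocks, arm totals need not be exactly 30; with blocks of 4 and 120 patients each arm lies between 27 and 33. No extra patients or visits are needed. Withholding upcoming assignments from enrolling staff and varying the block sizes are optional good practice and not part of this correction.
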